#### **Statistical issues**

## Analysis plan

Student's t test (for Intraoperative blood loss/blood transfusion, Length of stay in PACU) Wilcoxon rank-sum test (for Length of Stay in hospital, Length of Stay in ICU, MMSE, AVLT, Digital span, Color Word stroop, digit symbol substitution),

 $\chi^2$  test (for hypothermia incidence, Incidence of shiver, Surgical site infection: WIthin 30 days postoperative, Adverse cardiovascular events: Within 30 days postoperative, Incidence of postoperative cognitive disoerder at7day postoperative) will be used to compare the primary and secondary outcomes between groups.

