#### Methods

# Overview of design

This is a randomized, single-blinded, multi-center study clinical trial to determine both clinical outcomes of stratified warm strategy to prevent intraoperative hypothermia. Patients enrolled into this trial will be from elective major surgery population in PUMC Hospital, Beijing Hospital and Xuanwu Hospital from April 1, 2019 to March 31, 2021. We plan to enroll approximately 800 patients. We review the medical records and have a face-to-face interview to determine whether the patient is eligible for the study according to the inclusion and exclusion criteria. Hypothermia risk will be estimated through PREDICTOR model in all eligible patients. According to hypothermia risk level, these patients will be stratefied into high, moderate and low risk group. Patients in each group will be randomly categorize into warm group and control group. For controll group traditional passive warm was used, which means cotton blanket was used to prevent hypothermia. While, for active warm group, different warm strategy are used according to risk level, prewarm for 30min only for low risk patients, prewarm 30 min and fluid warm for moderate risk patients, prewarm and forced-air warm throughout operation and fluid warm for high risk patients. Temperature will be record though the operation. All participants were followed up every day after surgery until 6 month after operations. Any post operation complication will be recorded carefully.

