#### Sample size estimates

 $\alpha$  (two-sided) = 0.05, power (1- $\beta$ ) = 0.90 A previous study revealed that hypothermia incidence is 39.9%[2]. The control and warming group is 1:1. According to our preresearch Warming effect size = 0.36, 10% drop-out, 793 patients are required in total.

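### Blood loss and PACU, hospital and ICU stay are compared by unadjusted tests, leaving unused risk level, hospital and planned operation, all known before allocation

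*Combined protocol and SAP*

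**What the plan says.** The section headed Analysis plan gives each outcome a two-group test. For two of the outcomes here it specifies "Student's t test (for Intraoperative blood loss/blood transfusion, Length of stay in PACU"; for the other two, "Wilcoxon rank-sum test (for Length of Stay in hospital, Length of Stay in ICU". No covariate, stratum or hospital term is named there or anywhere else in the document.

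Three other places bear on the point:

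- Overview of design: "Patients enrolled into this trial will be from elective major surgery population", at three hospitals, with no single procedure named. Patients are stratified into high, moderate and low hypothermia risk and randomised within those levels.
- Overview of design, on screening: "We review the medical records and have a face-to-face interview to determine whether the patient is eligible".
- Plans for randomization and blinding: stratified blocked randomisation, with the allocation opened about an hour before the expected start of surgery and after consent.

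The section headed Secondary outcome lists all four outcomes. The sample size rests on hypothermia incidence alone, and no power is claimed for these four.

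**The concern.** Blood loss and length of stay can be expected to differ between operations and perhaps between hospitals and risk levels. A plain two-sample test leaves all of that variation in the error term. Randomising within risk level balances the arms on risk, but it improves the precision of the comparison only if the analysis uses the strata, and this one does not.

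All three factors are fixed before allocation. Risk level must be computed in order to randomise, and hospital is known. Because surgery is elective, records are reviewed at screening and the envelope is opened about an hour before surgery, the planned operation must be known too. Adjusting for such variables carries no risk of post-randomisation bias.

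What is at stake is precision on outcomes that speak to recovery benefit and for which the sample size secures no power.

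**Working it through.** **Inputs from the documents.** The sample size section gives "Warming effect size = 0.36, 10% drop-out, 793 patients are required in total", a two-sided 0.05 level, and states that "The control and warming group is 1:1". Evaluable patients: 793 × 0.90 = 713.7, so 713.7 / 2 ≈ 357 per arm.

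**The plan's own figure.** The 793 is for hypothermia incidence, and the scale of the 0.36 is not stated. Read as a relative reduction, the warmed rate is 0.399 × 0.64 = 0.255. At 90% power that needs 223 per arm, or 446 / 0.9 ≈ 496 in total. The other readings tried (relative risk, odds ratio, absolute difference, warmed-arm rate, standardised difference) do not give 793 at the stated level and power either. That is a separate matter. Here 793 serves only to set the number per arm.

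**Assumptions.** The documents give no SD, no target difference and no share of variance explained by operation (R²). I take a shift of 0.2 SD and R² from 0 to 0.30.

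**Formula.** Adjustment multiplies the residual SD by √(1 − R²). Approximate power is Φ(λ − 1.96), where:

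- for a t test or linear model, λ = 0.2 × √(357/2) / √(1 − R²) = 2.672 / √(1 − R²);
- for a rank test, λ is multiplied by √(3/π) = 0.977, giving 2.611 / √(1 − R²).

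| R² | λ, rank | Power, rank | λ, linear | Power, linear |
|---|---|---|---|---|
| 0 | 2.611 | 74% | 2.672 | 76% |
| 0.05 | 2.679 | 76% | 2.741 | 78% |
| 0.10 | 2.752 | 79% | 2.817 | 80% |
| 0.20 | 2.919 | 83% | 2.987 | 85% |
| 0.30 | 3.121 | 88% | 3.194 | 89% |

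The R² = 0 row is the plan as written. The gain is 2 to 4 points at R² of 0.05 to 0.10, and 9 to 14 points at 0.20 to 0.30.

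**Check by simulation.** Settings: 714 patients, six operation categories, log-normal stay, a shift of 0.21 SD on the log scale, 3,000 runs. Power of the plain rank-sum test against a rank test stratified by operation was 78% and 82% (R² 0.10), 77% and 85% (0.20), and 77% and 90% (0.30). Type I error was about 5% for both tests.

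**Outcomes with many zeros.** If 80% of patients had zero ICU days (an assumption), simulated power at R² = 0.20 rose only from 51% to 56% with six strata.

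**How many strata.** Six operation categories crossed with three risk levels and three hospitals make 6 × 3 × 3 = 54 cells, and 714 / 54 ≈ 13 patients each. Simulated power (0.2 SD shift, risk and hospital assumed non-prognostic, 1,000 runs):

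| R² | Plain rank-sum | 6 strata | 54 strata |
|---|---|---|---|
| 0 | 73% | 73% | 66% |
| 0.05 | 76% | 78% | 71% |
| 0.10 | 76% | 79% | 74% |
| 0.20 | 73% | 82% | 77% |
| 0.30 | 73% | 87% | 84% |

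Other simulations of the crossed test put its loss at R² = 0 at about 5 to 8 points. A main-effects model did not share the loss: it stayed at 75% at R² = 0, level with the plain test, and reached 83% at R² = 0.20.

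**The case against.** The strongest reply is that nothing here is an error. An unadjusted comparison in a randomised trial is a legitimate prespecified choice, these outcomes are secondary, and no power was promised for them. That stands: the point concerns efficiency, and the primary result is untouched.

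It can also be said that the size is assumed throughout. That stands too. The text available does not list the eligibility criteria, so the breadth of operations is inferred from the phrase about elective major surgery. If risk level partly tracks the operation, some of the gain shown belongs to risk level. This changes which factor earns the credit, but the planned tests use none of them.

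Two stronger readings are tempting:

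- A reader might infer that the unadjusted tests amount to discarding a sizeable fixed share of patients, say 20–40%. That share is simply the assumed R² under another name, and the documents give no R².
- A reader might infer that any adjustment is free even when the factors predict little. The 54-cell calculation shows otherwise for a fully crossed stratified test.

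**Conclusion.** The point holds as a loss of precision on four secondary outcomes. It is not a matter of bias or invalid tests, and a reader should not infer either: simulated type I error of the plain rank-sum test was about 5%.

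Under a 0.2 SD shift and 357 per arm, adjustment would raise rank-test power from about 74% to between 76% (R² 0.05) and 88% (R² 0.30). The true position in that range cannot be settled from the documents, and the gain is likely to be smaller for outcomes with many zeros. What does not depend on those assumptions is that the plan randomises within risk level and then ignores it, along with two other factors known before allocation.

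**What to change.** 1. Record planned-operation category before the envelope is opened, in a few broad groups defined in advance. Use the planned operation, not the one performed.
2. For these four outcomes, prespecify a regression with main effects for treatment, planned-operation category, risk level and hospital. Use proportional odds for hospital and ICU stay and for any outcome with many zeros, such as transfusion amount. Use a linear model, suitably transformed if skewed, for blood loss and PACU stay. A plain log scale is undefined at zero.
3. State the effect measure for each outcome, since an odds ratio and a mean difference answer different questions.
4. If a van Elteren test is preferred, stratify by the broad operation categories only, not by operation × risk × hospital cells.

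The cost is one extra data item, which the record should already hold, revised wording in the analysis plan and slightly more analysis work. No extra patients are needed.

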#### Plans for randomization and blinding

Randomization: Patients will be randomized using stratified blocked randomization. The random treatment assignments are placed in sealed, numbered, and opaque envelops who will not be involved in opening them. Two staffs signed and recorded the next unopened envelope before opening the envelope. Investigators will access the allocation about an hour before surgery is expected to start, after consent is obtained. Allocation will thus be remained concealed until the last practical moment.

Blinding: Patients are all blind to the allocation.

Reduce confounding factor: Patients in GA group were given 1.5-2mg/kg Propofol, 0.8mg/kg rocuronium, 2ug/kg fentanyl for induction of anesthesia. After tracheal intubation, anesthesia was continued with sevoflurane in 50% nitrous oxide with oxygen, and end-tidal anesthesia gas is maintained 0.9-1.2 MAC. Supplemental fentanyl doses of 50ug are administered for blood pressure elevation or heart rate increases amounting to more than 10% of baseline.

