#### Secondary outcome:

2. The amount of Intraoperative blood loss/blood transfusion

[Time Frame: During operation]

3. Length of stay in PACU

[Time Frame: Postoperative during in postanaesthesia care unit, up to 24 hours after surgery]

4. The incidence of Surgical site infection

[Time Frame: WIthin 30 days postoperative]

5. Lenght of Stay in hospital

[Time Frame: impatient period] up to 6 month after surgery]

6. Lenght of Stay in ICU

[Time Frame: impatient period, up to 6 month after surgery]

7. Incidence of Adverse cardiovascular events

[Time Frame: WIthin 6 month post operation]

8. Incidence of shiver

[Time Frame: during in postanaesthesia care unit. up to 24 hours after surgery]

9. Mini-Mental State Examination (MMSE),

It's a scare to evaluate cognitive function. Total score is 30. Higher values represent a better cognitive function.

[Time Frame: One day preoperation and 1, 7, 30 days postoperation]

10. digit symbol substitution test

The digit symbol substitution test is an evaluation tool used to assess cognitive functioning. It initially was part of the Wechsler Adult Intelligence Test (WAIS), a well-known test that measures an individual's attention. lower digit symbol test scores were correlated with a higher risk of developing dementia in both the five and 10 year groups. Higher values represent a better cognitive function.

[Time Frame: One day preoperation and 1, 7, 30 days postoperation]

11. Auditory Verbal Learning Test,

a memory test that involves learning verbal material, usually single words presented in a list, that is continually presented over repeated trials. Higher values represent a better memory functions.

[Time Frame: One day preoperation and 1, 7, 30 days postoperation]

12. Color Word Stroop Test

The Stroop Colour and Word Test (SCWT) is a neuropsychological test extensively used to assess the ability to inhibit cognitive interference that occurs when the processing of a specific stimulus feature impedes the simultaneous processing of a second stimulus attribute, well-known as the Stroop Effect. Higher values represent a better ability to inhibit cognitive interference.

[Time Frame: One day preoperation and 1, 7, 30 days postoperation]

13. digit span test.

a memory test that involves remember a series of numbers test short time memory Higher values represent a better memory functions.

[Time Frame: One day preoperation and 1, 7, 30 days postoperation]

14. postoperative cognitive dysfunction incidence

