- o Z score= (postoperative score-preoperative core) /SD of non-surgical group
- o Two or more than two item in cognitive examination Z score < -1.96
- Z score= (postoperative score-preoperative core) /SD of non-surgical group
  Two or more than two item in cognitive examination Z score < -1.96

[Time Frame: One day preoperation and 1, 7, 30 days postoperation]

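### The five cognitive scores get an unadjusted rank-sum test although a preoperative score is scheduled for each; a baseline-adjusted rank analysis would avoid a loss of precision whose size depends on an unstated correlation.

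*Combined protocol and SAP*

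**What the plan says.** Under Analysis plan, the scores "MMSE, AVLT, Digital span, Color Word stroop, digit symbol substitution" are assigned to the Wilcoxon rank-sum test. No covariate, change score or repeated-measures model is named for them, and no day is given. For the binary cognitive outcome the same section does fix a day: "Incidence of postoperative cognitive disoerder at7day postoperative".

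Under Secondary outcome, each of the five tests carries the same schedule: "Time Frame: One day preoperation and 1, 7, 30 days postoperation". So one preoperative and three postoperative scores are planned per test. MMSE is described as bounded: "Total score is 30. Higher values represent a better cognitive function".

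The only formula that uses the preoperative score is the one defining cognitive dysfunction: "Z score= (postoperative score-preoperative core) /SD of non-surgical group". That outcome is binary and goes to a chi-square test, so the formula does not settle how the five scores are analysed.

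Randomization is stratified ("Patients will be randomized using stratified blocked randomization"), with risk groups formed beforehand ("According to hypothermia risk level, these patients will be stratefied into high, moderate and low risk group"). The stratum does not enter the analysis either.

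**The concern.** A patient's preoperative score on a cognitive test usually predicts the postoperative score on the same test. If the analysis leaves it out, the differences between patients that were present before surgery stay in the error term. The trial would pay for the baseline measurement and then not use it for these five outcomes.

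The wording also leaves open which quantity is ranked. If the postoperative score is ranked, the baseline is unused. If the change is ranked, the baseline is used with a fixed weight of one, which is inefficient unless r is high and is worse than ignoring the baseline when r is below 0.5. Both readings are open, because the Analysis plan lists only test names while the one formula given for these scores is a difference.

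Five of the thirteen listed secondary outcomes are affected, and no power is stated for any of them.

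**Working it through.** **Inputs from the documents.** Two-sided alpha 0.05, 1:1 allocation, and "10% drop-out, 793 patients are required in total" (Sample size estimates). That total is for hypothermia incidence. The documents give no power, SD or correlation for the cognitive scores, so there is no figure of the plan's own to reproduce here. The total is used only to set a scale: 793 × 0.90 / 2 = 356.85, about 357 per arm.

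**Assumptions.** r = 0.3, 0.5, 0.7, 0.8; 357 per arm with scores at the visit compared; a difference for which the unadjusted test has about 80% power.

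**Closed form (linear approximation).** With equal variances before and after surgery, in units of the score variance:

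- postoperative score: 1
- change score: 2(1 − r)
- adjusted for baseline: 1 − r²

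Adjusted over postoperative is 1 − r². Adjusted over change is (1 − r²) / [2(1 − r)] = (1 + r)/2. Effective size per arm is 357 divided by the ratio. Power is Φ((1.960 + 0.842)/√ratio − 1.960).

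| r | ratio v. postoperative | 357 acts like | power | ratio v. change | 357 acts like | power |
|---|---|---|---|---|---|---|
| 0.3 | 0.91 | 392 | 84% | 0.65 | 549 | 93.5% |
| 0.5 | 0.75 | 476 | 90% | 0.75 | 476 | 90% |
| 0.7 | 0.51 | 700 | 97.5% | 0.85 | 420 | 86% |
| 0.8 | 0.36 | 992 | >99% | 0.90 | 397 | 84% |

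**Simulation, normal scores.** 10,000 runs per cell. Rank ANCOVA here is a regression of the ranked postoperative score on arm and ranked preoperative score. The shift is (1.960 + 0.842) × √(2/357) × √(π/3) = 0.2146 SD, which gives the rank-sum test on postoperative scores about 80% power.

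| r | rank-sum, postoperative | rank-sum, change | rank ANCOVA | linear ANCOVA |
|---|---|---|---|---|
| 0.3 | 80.5% | 65.2% | 83.4% | 85.3% |
| 0.5 | 79.4% | 80.1% | 89.1% | 91.2% |
| 0.7 | 79.8% | 94.9% | 96.9% | 98.0% |
| 0.8 | 80.1% | 99.2% | 99.3% | 99.7% |

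Type I error was 4.6-5.3% for all four tests. At the higher r the change-score comparison is near 100%, so the shift was reset to 0.2146 × √(2(1 − r)) = 0.254, 0.215, 0.166, 0.136 SD, which puts ranked change at about 80%. Rank ANCOVA then gives 93.4%, 89.4%, 84.7%, 82.1% against 79.7%, 80.8%, 80.2%, 80.5%: gains of about 14, 9, 4 to 5, and 2 points. At r = 0.9 and 0.95 rank ANCOVA is slightly below ranked change (78% v. 79%; 78% v. 81%).

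**Simulation, strongly skewed scores.** Lognormal with log-SD 1, the same 0.2146 shift on the log scale, r = 0.3, 0.5, 0.7, 0.8:

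- rank-sum on postoperative score: 80%, 79%, 80%, 81%
- rank-sum on change: 64%, 75%, 92%, 99%
- rank ANCOVA: 83%, 89%, 97%, 99%
- linear ANCOVA, two separate runs: 62-64%, 67-68%, 78-80%, 88-89%

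Rank ANCOVA agrees with the normal case by construction, because ranks do not change under a monotone transformation. Linear ANCOVA falls below at least one rank-sum reading at every r.

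**Simulation, MMSE capped at 30.** Scores rounded, latent SD 2, 6,000 runs per cell, same four values of r. With 23% at the ceiling, rank ANCOVA gains about 3, 8, 15, 19 points over ranked postoperative scores and 15, 12, 7, 5 over ranked change. With 50% at the ceiling the gains are 3, 6, 13, 17 and 17, 14, 9, 6.

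**The case against.** The sponsor can say that rank tests were chosen on purpose for bounded or skewed scores, since the same section uses t tests for blood loss and PACU stay. The outcomes are secondary and unpowered, and every gain quoted rests on an assumed r, an assumed 80% power and full attendance. If change is ranked, the baseline is already partly used, and on continuous scores the gain at r = 0.7-0.8 is only about 2 to 5 points.

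Much of this stands. It limits the size of the point and rules out linear ANCOVA as a blanket replacement. It does not justify leaving out the baseline, because a rank-based adjustment keeps the robustness of the planned test.

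Three stronger readings do not hold:

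- **That the planned test is invalid or biased.** Randomization protects the unadjusted comparison, and simulated type I error was close to 5%.
- **That linear ANCOVA is at least as powerful as either rank-sum reading whatever r is.** This holds for roughly normal scores only, and the documents give no distribution for any score. Besides the skewed case, heavy-tailed scores (t with 3 df, shift 0.24) gave linear ANCOVA 53%, 61%, 77%, 87% against 72%, 72%, 72%, 71% for ranked postoperative scores. Rank ANCOVA was not reported for that case.
- **That leaving out the risk stratum costs power here.** Stratum adjustment was not simulated, and no gain is claimed for it.

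**Conclusion.** The point holds as one of efficiency, not error. The plan schedules a preoperative score for each of five secondary outcomes, names no use of it in their comparison, and does not say what is ranked.

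If postoperative scores are ranked, a baseline-adjusted rank analysis is worth about 3 points of power at r = 0.3 and 17 to 19 at r = 0.7-0.8. If change is ranked, the order reverses: most at low r, little at 0.8, nothing or a slight loss at 0.9 and above. At r = 0.5 the gain is about 9 to 10 points under either reading on continuous scores. In the cases run, rank ANCOVA was at least level with both readings over r = 0.3 to 0.8 on normal, skewed and ceiling-limited scores, so the choice does not need a precise guess at r within that range.

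These figures are illustrative. They rest on the assumed correlations, on 357 per arm at the visit analysed, and on the simulated distributions. The change is worth making because it costs little; the primary conclusion of the trial does not depend on it.

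**What to change.** Analyse each postoperative cognitive score by a baseline-adjusted rank method, either rank ANCOVA or a proportional-odds model, with the preoperative score on the same test as covariate. Keep the rank-sum test as a sensitivity analysis and state whether it ranks the postoperative or the change score. Where the score distribution allows it, add a linear ANCOVA adjusted mean difference with 95% CI as a supporting estimate. State how patients without a preoperative score are handled.

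The cost is a few sentences in the Analysis plan and a few lines of code, with no new data or visits. The downsides are a modelling assumption and an effect on the rank or odds scale that is less direct to interpret; the supporting mean difference helps with the second. Which postoperative day is principal, and whether to adjust for risk stratum, are separate decisions.

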## **Research Designing**

# Specific aim

To determine the efficacy of different warming method according to hypothermia risk estimation to prevent perioperative hypothermia and reduce perioperative complications.

[figure not shown]

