#### Measurements

Intervention: traditional cotton blanket warm vs. active warm according to risk level

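### The primary chi-square names no stratification although randomisation is within three risk levels, each with its own regimen; it is valid but conservative, and no estimate by risk level is planned.

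*Combined protocol and SAP*

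**What the plan says.** **Design.** In Overview of design, a hypothermia prediction model is applied to every eligible patient and "these patients will be stratefied into high, moderate and low risk group". Then "Patients in each group will be randomly categorize into warm group and control group". In the warm arm the regimen depends on the level: "prewarm for 30min only for low risk patients, prewarm 30 min and fluid warm for moderate risk patients", with a third, more intensive regimen for high risk. Plans for randomization and blinding adds "Patients will be randomized using stratified blocked randomization" without naming the stratification factors; Overview of design supplies risk level.

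**Question.** The Specific aim reads "To determine the efficacy of different warming method according to hypothermia risk estimation". Measurements describes the intervention as "traditional cotton blanket warm vs. active warm according to risk level". Sample size estimates sizes a single two-arm comparison: "The control and warming group is 1:1".

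**Analysis.** The Analysis plan assigns a chi-square "test (for hypothermia incidence, Incidence of shiver, Surgical site infection: WIthin 30 days postoperative" and the remaining binary outcomes, compared between groups. It lists tests only. No stratified test, model adjusting for risk level, effect estimate with confidence interval, result by level or interaction test appears in the document.

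**The concern.** There are two separate problems.

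1. **Efficiency.** The stratification factor is a prediction of the primary outcome, so hypothermia incidence should differ between levels. Stratified randomisation removes the between-level variation from the treatment comparison. An unstratified chi-square still counts that variation in its standard error, which makes the standard error too large. The result is a type I error below 5% and some loss of power.

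2. **An unanswered reading of the aim.** The pooled comparison averages three different regimens. It answers whether risk-guided warming beats a cotton blanket overall. It does not show what each regimen did at its own level, and changing the primary test would not show that either. If results by level are chosen only after the data are seen, they become post-hoc subgroups.

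**Working it through.** **Inputs from the plan.** Two-sided alpha 0.05, power 0.90, 1:1 allocation, overall hypothermia incidence 39.9%, effect size 0.36 (scale not stated), 10% drop-out, total 793.

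**The plan's own figure.** 793 did not reproduce at 90% power under any reading of 0.36 that was tried. A 36% relative reduction (39.9% to 25.5%), for example, needs 223 per arm, 446 in total and 496 with drop-out. That is a separate matter. Here 793 only fixes the number of completers: 793 × 0.9 ≈ 714, and 714 / 6 = 119 per arm per level if the levels are equal.

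**Assumptions.** The plan gives no shares or rates by level. Control rates are taken as 30/40/50, 20/40/60 or 10/40/70% (low/moderate/high), each averaging 40%.

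**Why the chi-square is conservative.** With 1:1 allocation inside each level, the expected events in the warm arm are half the total whether computed pooled or by level. The pooled Pearson and Cochran-Mantel-Haenszel (CMH) statistics therefore have the same numerator and differ only in variance. For equal levels:

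ratio = mean of p(1−p) within levels / [p̄(1−p̄)]

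- 30/40/50: mean(0.21, 0.24, 0.25) / 0.24 = 0.972
- 20/40/60: mean(0.16, 0.24, 0.24) / 0.24 = 0.889
- 10/40/70: mean(0.09, 0.24, 0.21) / 0.24 = 0.750

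The actual type I error is 2[1 − Φ(1.96/√ratio)] = 4.7, 3.8 and 2.4%.

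**Simulation** (100,000 trials per scenario, no continuity correction; chi-square v CMH, %; odds ratios apply within each level):

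| Control rates | Type I error | 36% relative reduction | OR 0.60 | OR 0.64 |
|---|---|---|---|---|
| 30/40/50 | 4.8 v about 5 | 98.5 v 98.6 | 88.6 v 89.1 | 79.2 v 80.1 |
| 20/40/60 | 3.9 v about 5 | 98.8 v 99.0 | 84.1 v 86.7 | 72.8 v 76.5 |
| 10/40/70 | 2.5 v about 5 | 99.2 v 99.5 | 73.0 v 81.4 | 60.0 v 70.6 |

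At OR 0.36 both tests have power of about 100%.

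**Unequal levels** (per arm 60/178/119, 178/119/60 or 60/119/178). At OR 0.64 the loss is 2–3 points for 20/40/60 and 5–10 points for 10/40/70; chi-square type I error is 2.4–4.2%.

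**What a pooled result can hide.** Suppose the low-risk regimen does nothing: control 20/40/60% v warmed 20/35/30%. Chi-square power is 91.8% and CMH 92.5%. Either test would very probably be positive without revealing the ineffective regimen. This supports estimates by level, not the change of test.

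**Precision by level** (119 per arm). Half-width = 1.96 × √[p₁(1−p₁)/119 + p₂(1−p₂)/119]. For 20% v 12.8%: 1.96 × √[(0.160 + 0.112)/119] ≈ 9.4 points. Across scenarios it is about 9–13 points for control rates of 20–70% and 7–8 points at 10%. Power within one level for a 36% relative reduction is 17, 32, 66 and 92% at control rates of 10, 20, 39.9 and 60%.

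**The case against.** The strongest reply is that nothing is invalid. False positives are controlled, and the pooled test answers the question that Measurements and Sample size estimates describe. If 0.36 means a 36% relative reduction or an odds ratio of 0.36, stratifying gains almost nothing. This stands, and it is why the point is an improvement and not a defect of validity.

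Second, the 11-point figure needs the steepest assumed gradient and a within-level OR of 0.64. The pooled rates are then 40 v 32.1%, an overall OR of (0.321/0.679)/(0.40/0.60) ≈ 0.71. Holding the overall OR at 0.64 (40 v 29.9%) gives chi-square v CMH power of 81.2 v 82.0, 82.2 v 85.1 and 84.1 v 89.8%, a gap of about 1 to 6 points. This also stands as a qualification: 11 points is the upper end. With no gradient, the two tests perform alike.

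Third, the plan does not literally say unstratified; CMH is itself a chi-square test, and the plan uses the word group for both arms and risk levels. But no stratification is named and only one two-arm comparison is sized. If a stratified or by-level analysis was intended, the SAP still has to say so.

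Fourth, the trial is not sized for results by level, and an interaction test cannot separate regimen from baseline risk. Both are true. They limit what may be claimed; they do not justify planning no estimates.

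**Conclusion.** The concern holds. The planned primary test is valid for the overall comparison, and conservative to the extent that incidence differs by risk level. In the equal-level scenarios, type I error falls from 4.8% with a mild gradient to 2.5% with a steep one. The power cost runs from under 0.5 points for a large effect to about 11 points for a modest effect with sharply separated levels. Where in that range the trial lies cannot be settled from the plan, which gives neither rates and shares by level nor the scale of its effect size.

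The absence of any effect estimate with a confidence interval, overall or by level, is the more consequential part. It does not depend on those assumptions, and it leaves the per-method reading of the Specific aim unaddressed. The plan should be changed, but a positive result under the current test would still stand.

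**What to change.** - **Primary test:** CMH stratified by risk level. Add hospital if it is a randomisation stratum; the randomisation section should name the factors.
- **Primary estimate:** a Mantel-Haenszel risk difference or risk ratio with 95% CI. The SAP should name one in advance.
- **Binary secondary outcomes:** the same stratified approach. The t and Wilcoxon tests for the other outcomes raise the same question, which was not quantified here.
- **By risk level (secondary, descriptive):** the warm-v-control difference with 95% CI in each level.
- **Interaction:** one treatment-by-risk-level test on a scale named in advance, such as the odds ratio. Scale matters: under a constant 36% relative reduction, the 2-df test is significant in 36% (20/40/60) and 80% (10/40/70) of trials on the risk-difference scale, against 10% and 19% on the odds-ratio scale (40,000 simulated trials).
- **Limits to state:** regimen is fully tied to risk level, so the interaction cannot separate the two. Claims about a regimen should rest only on the estimate from its own level.

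The cost is SAP wording and a few lines of code, with no new data or patients. The drawbacks are slightly more analysis work, wide intervals by level, low power in the low-risk level and an interaction result that depends on scale. The SAP should state them.

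### Cognitive dysfunction incidence is listed at days 1, 7 and 30, but the analysis plan compares it at day 7 only and gives days 1 and 30 no role

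*Combined protocol and SAP*

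**What the plan says.** The Secondary outcome section lists "14. postoperative cognitive dysfunction incidence". A patient meets the definition when the condition "Two or more than two item in cognitive examination Z score < -1.96" is satisfied. Each Z score is the change from the preoperative score divided by a standard deviation from a non-surgical group. The time frame attached to the outcome is "Time Frame: One day preoperation and 1, 7, 30 days postoperation".

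The Analysis plan puts POCD among the chi-square outcomes, as "Incidence of postoperative cognitive disoerder at7day postoperative". It says that the tests it names "will be used to compare the primary and secondary outcomes between groups". The same sentence assigns a Wilcoxon rank-sum test to the component scores, "MMSE, AVLT, Digital span, Color Word stroop, digit symbol substitution", without naming a day.

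No other section gives an analysis of POCD at day 1 or day 30, or says that those days are descriptive, exploratory or dropped.

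**The concern.** The Analysis plan presents itself as covering the listed outcomes, yet for POCD it covers one of three listed postoperative days. Day 30 is the last POCD assessment and the only listed one that bears on whether an early difference persists. Followed as written, the plan allows a day-7 difference to be reported with no planned check of whether it lasts, and a difference seen only at day 30 has no planned comparison.

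Because the outcome list includes days 1 and 30 and the analysis list is silent on them, those results could be left out, or reported selectively, without departing from the Analysis plan. A reader comparing the two sections cannot tell what status these days were meant to have.

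**Working it through.** The documents give no sample size, power or error rate for POCD, so there is no figure to reproduce. The check sets the two sections side by side.

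| Item | Secondary outcome section | Analysis plan |
|---|---|---|
| POCD incidence, day 1 | listed | no comparison stated |
| POCD incidence, day 7 | listed | chi-square |
| POCD incidence, day 30 | listed | no comparison stated |
| Five component scores, days 1, 7, 30 | listed | Wilcoxon, no day named |

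**Count.** Listed postoperative POCD assessments: 3. With a planned between-arm comparison: 1. Without: 3 − 1 = 2, that is 2 of 3.

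**The preoperative visit.** The POCD time frame also includes the day before surgery. The Z score is a postoperative score minus the preoperative score, so that visit supplies the baseline and cannot itself yield a POCD event. It is not counted above.

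**Is the day-7 limit just shorthand?** Within one sentence the component scores carry no day and POCD carries one, so the limit is explicit. Adverse cardiovascular events show a similar mismatch: the Secondary outcome section runs to 6 months, while the Analysis plan tests within 30 days. Two outcomes for which the analysis window is narrower than the listed one suggest that the sections were not reconciled.

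**Would testing every day at 0.05 repair it?** For three independent tests, the chance of at least one false positive is 1 − (1 − 0.05)³ = 1 − 0.857 = 0.143. Independence is assumed for illustration; repeated assessments of the same patients are positively correlated, so the true value would be lower. A Bonferroni split would be 0.05 / 3 = 0.0167 per test. Simply adding unadjusted tests is therefore not the remedy; each day needs a stated role.

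**The case against.** The strongest reply is that limiting a composite secondary outcome to one prespecified day is legitimate and avoids multiplicity. The time frame can also be read as a testing schedule: the same wording is attached to each of the five cognitive tests, and it includes a day on which POCD cannot occur. On that reading the schedule is merely wider than the analysed day.

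Much of this stands. Choosing day 7 is defensible, and the point does not ask for it to change. But the time frame is attached to POCD incidence as an outcome in its own right, and even on the schedule reading nothing says what happens to POCD at days 1 and 30.

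Three stronger readings are tempting, and the documents do not support them:

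- *A reader might infer that the day-1 and day-30 assessments are never compared or go unused.* The component scores are listed outcomes at all three days, and their Wilcoxon test has no day restriction, so the plan leaves those comparisons open. Only the POCD classification is confined to day 7.
- *A reader might infer that day 7 may not have been chosen in advance.* It is the only POCD day that the Analysis plan names, so it is prespecified. What is missing is the status of the other two days.
- *A reader might infer that using more days would buy substantial precision.* That needs a common effect averaged over days. An arm difference that may fade or emerge by day 30 is not a common effect, and a day-7 contrast from a model with arm-by-day terms rests essentially on day-7 data when data are complete. The documents give neither a POCD incidence nor a within-patient correlation from which to size any gain.

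**Conclusion.** The point holds in a limited form. For POCD incidence the outcome list and the analysis plan disagree: two of the three listed postoperative days, including the last, have no prespecified between-arm comparison and no stated role. It is a minor issue in one of the 13 numbered secondary outcomes (items 2 to 14), with no effect shown on the primary outcome or the sample size.

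The conclusion rests on reading the time frame under POCD as belonging to that outcome, and on the Analysis plan being the full list of planned comparisons, as its own wording indicates. It needs no assumption about POCD rates or correlations.

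**What to change.** In the Analysis plan:

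- Name day 7 as the main POCD contrast.
- State that the arm difference in POCD incidence at days 1 and 30 will be estimated with 95% confidence intervals, as supportive results without separate significance claims.
- Adjust for the hypothermia-risk stratum used in randomisation. One option is a single logistic GEE with arm, day, arm-by-day and stratum. Stratum-adjusted analyses at each day would serve equally well.

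In the Secondary outcome section, make the POCD time frame match: days 1, 7 and 30 as outcome days, with day 7 marked as main and the preoperative visit as baseline only.

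The cost is a few lines of SAP text, a stratum-adjusted analysis in place of one chi-square test, and two more reported estimates. The assessments are already scheduled. The fix depends on a separate matter: the Z score needs a standard deviation from a non-surgical group, and the Overview of design describes no such group. Until the source of that value is settled, POCD cannot be computed as defined on any day.
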